7. Infected wounds or osteomyelitis (confirmed by bone biopsy, MRI or bone scan).
8. Active Charcot as described by Saunder's classification system.
9. Poor nutritional status, Albumin level < 2.9.
10. Ulceration size less than 1.0 cm² or greater than 20 cm².
11. Porcine allergy.
12. Chemistry tests serum creatinine, 2 times above the upper limits and LFTs 3 times above the upper limits.

TREATMENT: Total duration of study per subject: Up to 22 weeks (Includes to 2 weeks of screening and up to 12 weeks until the end of the follow-up period).

DURATION OF ADMININSTRATION: 8 weekly applications (starting at Visit 4/Week 1).

STUDY DESIGN: This is a randomized, single-blinded, four-armed controlled clinical equivalence trial comparing the effectiveness of three intervention arms (acellular ECM, Oasis® and a cellular ECM, fibroblast-only Dermagraft®) and a standard treatment arm.

EFFICACY ENDPOINTS:

PRIMARY EFFICACY OUTCOME

1. Complete closure of ulcer by Week 12

SECONDARY EFFICACY OUTCOME

1. Complete closure of ulcer by Week 20
2. Rate of ulcer healing

3. Cost effectiveness comparing Oasis® and Dermagraft®

QUALITY OF LIFE ASSESSMENT: We will also evaluate the cost-effectiveness of the Oasis® compared to Dermagraft® and the standard of care by measuring QALYs as the measure of effectiveness, based on results obtained from SF-36v2™ questionnaire. Multiple regression will be used to allow to evaluate continuous dependent variable outcomes, including change scores between baseline and end of study physical (PCS) and mental (MCS) component summaries from the SF-36v2TM questionnaire.

DATA ANALYSIS: The primary outcome is wound closure by Week 12, will use Chi-square test to compare the percentages of subjects with complete closure in each group. Exploratory analysis with logistic regression, using the complete closure at 12 weeks as the dependent variable and the independent variables would include, treatment, size of ulcer, location on foot, how long ulcer has been present, previous revascularization, offloading compliance, concomitant medications, foot deformity, history of amputation, diabetes complications index, CRP level, and glucose control (HbA1c). Selection of covariates will be performed by stepwise modeling procedures.

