4.2 DESCRIPTION OF STUDY GROUPS

Standard (Conventional) Therapy:

Standard therapy will consist of the typical foot evaluation and care provided by the Department of Veteran Affairs facilities, which will include weekly sharp debridement, cleansing of wound with normal saline, and application of non-adhesive dressing (Adaptic® or Mepitel®), Iodosorb® gel over wound bed, covered by dry dressings. The investigator will document the standard care provided during clinic visits including weekly follow-up evaluations. Offloading will be standardized, which will involve placement in modified offloading insert (trilaminar plastazote) and removable Cam Walker boot.

Oasis®:

Patients in the Oasis® group will undergo the same wound care and offloading modality as the Standard Therapy group, with weekly wound evaluation dressing changes. The Oasis® matrix will be applied on the wound (cut to size), moistened with normal saline to assure adherence to wound bed, then apply non-adhesive dressing (Adaptic® or Mepitel®), moist sterile gauze, dry and gauze dressings. Up to 8 weekly applications will be applied to wound until healed.

Dermagraft®:

Patients in the Dermagraft® group will receive the same Standard Therapy, with weekly wound evaluation and dressing changes. The Dermagraft® will be thawed as directed by the manufacturer, then under sterile technique Dermagraft® will be cut to size of wound, covered with non-adhesive coverage (Adaptic® or Mepitel®), moistened sterile gauze and dry dressings. Up to 8 weekly applications will be applied to wound until healed.

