- Changes in concomitant medications, adverse events, compliance to offloading, will be recorded.
- If ulcers heal sooner than 8 weeks, the subject will be assessed the following week. Ulcer healing is defined by 100% epithelization as determined by the clinician. The subject with healed ulcer will also return for follow-up visits Weeks 9, 16, 20.

NOTE: if ulceration remains open after 8th application – then will switch back to standard of care therapy (if budget allows, may consider extending graft course).

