4.3.4 Study Endpoint (Visit 19/Week 16)

- Subjects to complete the health-related quality of life survey, the Medical Outcomes Study 36 item Short Form (SF-36v2™) health survey.
- Vital signs will be obtained and recorded.
- The ulcer will be assessed – visual inspection – complete ulcer characteristics form (see appendix). Determine if reaches 100% epithelization determined by clinician.
- Labs drawn from each subject, hematological and chemistry panel. Pregnancy test of childbearing age.
- If concern for infection, confirmatory bacterial culture will be obtained (deep swab culturette or tissue specimen/biopsy). Radiographical x-rays and blood work (CBC, ESR, CRP, and Chem) may also be performed if deemed necessary by investigator clinician.
- Digital imaging of ulcer location, if remains non-healing then 2 images to be obtained prior to and after surgical debridement.
- Surgical debridement of ulcer if not healed, will be performed using curette or blade and standard therapy.
- Changes in concomitant medications, adverse events, compliance to offloading, will be recorded.

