6 STATISTICAL DESIGN

Measures:

Measures will be collected at baseline, weekly thereafter, with primary endpoint of complete healing at Week 12, and final secondary endpoint measurement at Week 20. The ulcer will be assessed weekly and will be treated as described above. A designated inter-observer will be at each of the testing sites, (blinded to the treatment of the subjects) which will perform all measurements. The following measurements will be taken: size (surface area calculation), photos (digital includes ruler) and complete foot ulcer assessment (description of ulcer/characteristics), before and after debridement. Subjects where ulceration healed earlier than Week 12 will have follow-up assessment one week after healing, then at Week 12 and 20. If ulcerations healed after 12 weeks, then the subjects will be assessed at one week after healing and at Week 20. There will be 4 follow-up visits (Weeks 17, 20, 24, 28), assessed every 4 weeks for a total of 16 weeks.

During the study, if ulceration appears to be infected as determined by clinical presentation characterized by the presence of two or more signs of inflammation,³ the clinician will follow the protocol of obtaining wound culture for microbiology, radiographs, blood work (CBC, chemistry panel, sedimentation rate, and C-reactive protein), and treatment immediately with appropriate antibiotics. Subjects with infected ulcers will be withdrawn from study and investigators will be notified. In addition, adverse events will be well documented and treated per protocol, and subjects will be withdrawn from study.

Clinical Outcomes:

- The percentage of subjects that have complete closure of ulceration by Week 12 and Week 20. Complete healing will be defined as full re-epithelialization with no drainage, or callus formation and remains closed after 1 week of wound closure.
- Rate of wound healing to achieve complete closure. Weekly measurements of surface area will be recorded on a grid marked acetate sheet, using a metric ruler to determine length and width of the wound.
- A diabetic foot ulcer assessment form will be filled out at weekly follow-up visits, that describes characteristics of ulceration including peri-ulcer erythema, wound margins, fibrin, granular tissue, peri-ulcer pruritus, edema and location, pain, amount of drainage and type, amount of epithelialization, pain level, depth, and bioburden.

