We will perform a cost-effectiveness analysis comparing the treatment groups Dermagraft®, Oasis® and the standard care group at the NCHCS using ANOVA or Kruskal-Wallis test depending if data is normally distributed for comparison of the three treatment arms. If significant, we will further analyze with pair-wise comparisons by using t-test or Wilcoxon rank-sum test with the Bonferroni correction to control for type I experiment-wise error rate of 0.05. A p-value less than $0.05/3 = 0.0167$ will be considered statistically significant.

We will evaluate the cost-effectiveness of the Oasis® compared to Dermagraft® and the standard of care by measuring QALYs as the measure of effectiveness, based on results obtained from SF-36v2™ questionnaire. Multiple regression will be used to allow to evaluate continuous dependent variable outcomes, including change scores between baseline and end of study physical (PCS) and mental (MCS) component summaries from the SF-36v2™ questionnaire.

Rates of healing among the three groups will be analyzed using log-rank test to compare time of healing within 20 weeks among the 3 treatment groups.

Secondary endpoint (complete healing at 20 weeks), recurrence ulceration rate at 20 weeks will be analyzed using Chi-square tests. In addition, demographics, smoking history, and characteristics of the wound will also be summarized in table. Data that are continuous variables will be summarized by using mean, median, standard deviation, coefficient of variation, minimum and maximal values. Frequency tables will summarize categorical variables.

Timeline and Milestones:

Months	Year 1		Year 2	
	1-6	7-12	1-6	7-12
Aim 1: Recruitment				
Step 1: Screening (2-week run-in phase)	✓	✓	✓	
Step 2: Randomization/Assignment	✓	✓	✓	
Aim 2: Data Collection				
Step 1: Healed by Week 12	✓	✓	✓	✓
Step 2: Wound not healed by Week 12, continue in study until Week 20	✓	✓	✓	✓
Step 3: If wound has not reached closure beyond the 8 weeks of Dermagraft® – will switch to standard of care (expensive). Oasis® – continue to the end of study	✓	✓	✓	✓
Aim 3: Data Analysis				
Step 1: Outcome effectiveness If outcome show significant difference will cross over for intent-to-treat	✓	✓	✓	✓

7 References

1. Vista/CPRS data record system from 2006-2008, retrieved on 4/7/2009.
2. Vista/CPRS data record system from 2006-2008, retrieved on 4/7/2009.

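### Step 3 of the Section 6 timeline can be read as letting Oasis run past the eight-application cap that stops Dermagraft, and the budget extension in Section 4.3.3 does not require equal courses

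*Combined protocol and SAP*

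**What the plan says.** The treatment sections are consistent. Section 4.2 states the cap once under Oasis and once under Dermagraft, in the same words: "Up to 8 weekly applications will be applied to wound until healed". Section 4.3.3 repeats it under each product. The Protocol Summary gives the duration of administration as "8 weekly applications (starting at Visit 4/Week 1") without separating the products. The flow chart in Section 4.3 marks the two grafts identically, at Week 0 and Weeks 1 to 7 and at no later visit. The note closing Section 4.3.3 says "if ulceration remains open after 8th application – then will switch back to standard of care therapy", again naming no product.

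Two other pieces of text do not fit this.

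- Section 6, Timeline and Milestones, Aim 2 Step 3 limits only Dermagraft to eight weeks. An unclosed wound on Dermagraft "will switch to standard of care (expensive). Oasis® – continue to the end of study".
- The Section 4.3.3 note adds, in parentheses, "if budget allows, may consider extending graft course". It gives no product, no criterion, no maximum and no rule that the two grafts be handled alike.

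Nothing in the document reconciles Step 3 with the cap.

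**The concern.** Step 3 stops one product and gives its expense as the reason. It then says that the other product continues. Read naturally, the cheap graft goes on being applied after the costly one has stopped. The primary endpoint is at Week 12, several weeks after an eight-application course ends, so a longer Oasis course could act on the primary comparison as well as on Week 20 closure, time to healing and cost.

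Oasis versus Dermagraft is the contrast behind the adoption decision in Sections 1 and 2. If extra Oasis helps closure, a product that is less effective over eight applications could look equivalent because it was given for longer. Oasis versus standard care would likewise test a longer regimen than Section 4 describes. Dermagraft versus standard care is not touched by Step 3.

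The budget clause raises the same problem by another route. Section 3 says that the treating clinician can identify the product, and Section 2 prices an application at $1800 for Dermagraft and $80 for Oasis. A decision driven by budget could therefore easily fall on one product only.

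**Working it through.** **Inputs.** Planned closure by Week 12 is 50% in each graft arm and 25% under standard care, with 57 subjects per arm, 80% power and significance level 0.05 (Section 6, Sample Size Estimation). Assumed dropout is 20% (Section 3, which does not say whether 57 is before or after dropout). Prices are $80 and $1800 per application (Section 2).

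**The plan's own figure.** The pooled chi-square formula without continuity correction, two-sided (sidedness is not stated), is n = [z(0.975)·√(2p̄(1−p̄)) + z(0.80)·√(p₁(1−p₁)+p₂(1−p₂))]² / (p₁−p₂)². With p₁ = 0.25, p₂ = 0.50 and p̄ = 0.375:

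(1.960 × 0.6847 + 0.8416 × 0.6614)² / 0.0625 = 57.7, or 58 rounded up.

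The stated 57 reproduces to within rounding. Nothing in this point changes it.

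**Maximum course under each rule.**

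| Rule | Oasis | Dermagraft |
|---|---|---|
| Protocol Summary, Sections 4.2, 4.3 and 4.3.3 (main clause) | 8 | 8 |
| Step 3, read as continued application | more than 8 | 8 |
| Step 3, read as follow-up only | 8 | 8 |
| Budget extension | no limit stated | no limit stated |

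**Extra weekly applications.** The flow chart places the eight doses at Weeks 0 to 7; the Protocol Summary places them at Weeks 1 to 8.

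- Before Week 12: Weeks 8 to 11 give 4 extra, or Weeks 9 to 11 give 3.
- Through Week 15, the last weekly visit of the treatment phase: Weeks 8 to 15 give 8 extra, or Weeks 9 to 15 give 7.

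The closure definition requires that the ulcer "remains closed after 1 week of wound closure". If that confirmation must fall by Week 12, closure has to be in place by Week 11. Then only 3 (Weeks 8 to 10) or 2 (Weeks 9 to 10) of the extra applications can act on the primary endpoint.

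**Subjects exposed.** Still open at Week 12, before dropout: 0.50 × 57 = 28.5, about 28. If 20% leave evenly across healed and unhealed subjects: 0.8 × 28.5 = 22.8. Withdrawals for infection or adverse events beyond that would lower it further.

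The number open at the eighth application is larger, because it includes those who close between then and Week 12. The documents give no closure rate at Week 8, so the possible range before dropout is 28.5 (no closures after Week 8) to 57 (none before it). As an illustration only, assume a constant closure hazard that reaches 50% at Week 12. The fraction open at Week 8 is then 0.5^(8/12) = 0.63, and 0.63 × 57 ≈ 36. Subjects who close between Weeks 8 and 12 would get fewer extra applications than those who stay open.

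**Product cost per subject, same horizon (through Week 15) for both.**

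| | Planned 8 | Extra 7 to 8 |
|---|---|---|
| Oasis | 8 × $80 = $640 | $560 to $640 |
| Dermagraft | 8 × $1800 = $14,400 | $12,600 to $14,400 |

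Under Step 3 the Oasis total would be at most $640 + $640 = $1,280, against $14,400 for Dermagraft. Step 3 does not tie the end of the study to a week: Week 16 is headed as the study endpoint, Step 2 runs to Week 20, and the last visit is Week 28. Weekly Oasis from Week 1 to Week 20 would be 20 × $80 = $1,600. That is an upper bound for that period, because no visit is scheduled between Weeks 17 and 20. The ranking on product price does not change.

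**The case against.** The best defence is that the operative rule is not in doubt. The cap appears separately under each product, and Step 3 is one cell of a project timeline, filed under data collection. The Measures text in the same Section 6 defers to the treatment sections: "The ulcer will be assessed weekly and will be treated as described above". Step 2, just above Step 3, uses the same verb for staying in the study, so Step 3 may mean only that Oasis subjects remain under observation.

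Much of this stands. A reader might infer that the protocol prescribes a longer Oasis course, or that the comparison is already biased. The documents do not support that: the line never mentions applications, and staff who follow Section 4 give eight and eight. The follow-up reading is nevertheless the weaker one. Step 2 already keeps unhealed wounds in the study to Week 20 without distinguishing arms, so a follow-up line for Oasis alone would add nothing, and expense is a reason to stop applying a product, not to stop observing a patient.

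A second defence is that Step 3 merely applies the budget extension: affordable for Oasis, too costly for Dermagraft. That would remove the contradiction but leave the courses unequal, by choice.

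A reader might also take Sections 4.3.4 and 4.3.5 as proof of conflict, since from Week 16 they say "Surgical debridement of ulcer if not healed, will be performed using curette or blade and standard therapy" with no exception for Oasis. This is weak evidence. Standard care is the background in every arm, so prescribing it does not by itself exclude Oasis.

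**Conclusion.** The concern holds as a conflict on the more natural reading of Step 3, together with an extension clause that does not protect equal treatment. It is not established that unequal courses were intended or given. If Step 3 is followed, or the extension is used for one product only, Oasis versus Dermagraft mixes product with treatment length at Week 12, at Week 20, in time to healing and in cost. If Section 4 is followed and no extension is used, there is no bias from this source.

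The size rests on the planned 50% closure and weekly dosing: about 28 of 57 Oasis subjects open at Week 12 before dropout, and 3 to 4 possible extra applications before then. The 28 should not be taken as the number open at the eighth application, which is higher and not given. How far extra applications would move closure cannot be derived from the documents. Nor do the figures support an inference that Step 3 would reverse the product-price ranking. The wording should be corrected, since the contrast affected is central to the trial.

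**What to change.** Replace Step 3 with: *If the wound has not closed after the 8th application of Dermagraft or Oasis, switch to standard of care and continue scheduled assessments.* In the Section 4.3.3 note, delete the budget extension, or bind it to one criterion and one maximum number of applications that are identical for both products. If subjects have already been treated, report the number of graft applications per subject by arm and any use of the extension, so that a reader can see whether the courses differed.

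The main fix changes wording in two places and leaves the sample size and visit schedule alone. Its cost is the loss of the ad hoc option to extend grafting. Keeping an equal extension instead would also mean editing the cap in the Protocol Summary, Section 4.2, the flow chart and Section 4.3.3.

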8 APPENDIX

Ulcer Characteristic Form

Size: Dimensions _____ x _____ x _____ cm

Location of Foot Ulcer:

- A. Dorsal foot
- B. Plantar digits (1, 2, 3, 4 or 5)
- C. Plantar forefoot (excludes digits)
- D. Plantar midfoot (cuneiform, navicular level)
- D. Plantar heel

Wound Bed/Base:

Percentage of Granulation (Red) Tissue

- A. Bright, beefy red; 75% to 100% of wound bed
- B. Bright, beefy red; Greater than 50% to less than 75% of wound bed
- C. Pink, dull red; Greater than 25% to less than 50% of wound bed
- D. No granulation tissue present and/or less than 25% of wound bed

Percentage of Fibrinous (Yellow) Tissue

- A. None
- B. Less than 25% of wound bed
- C. 25% to less than 50% of wound bed
- D. 50% to less than 75% of wound bed
- E. 75% to 100% of wound bed

Percentage of Necrotic (Black/Eschar) Tissue

- A. None
- B. Less than 25% of wound bed
- C. 25% to less than 50% of wound bed
- D. 50% to less than 75% of wound bed
- E. 75% to 100% of wound bed

Epithelialization (appearance of skin – may appear pink or red skin):

- A. Less than 25% of wound bed
- B. 25% to less than 50% of wound bed
- C. 50% to less than 75% of wound bed
- D. 75% to less than 100% of wound bed
- E. 100% all intact skin

Wound Edges/Margins:

- A. Healed
- B. Greater than 50% advancing epithelialization of wound edges
- C. Less than 50% advancing epithelialization of wound edges
- D. No advancing border of epithelium

Depth:

- A. None – intact skin
- B. Partial thickness involving skin loss of epidermis and/or dermis
- C. Full thickness involving skin loss of epidermis/dermis and subcutaneous layer

- D. Tendon/joint capsule exposed
- E. Probes to bone

Peri-wound Erythema:

- A. Normal, no appearance of redness/pinkness
- B. Mild pinkness surrounding wound
- C. Bright red and/or blanches to touch
- D. Pallor, pale
- E. Violaceous, dusky red and or non-blanchable
- F. Black, necrosis

Peri-wound Edema:

- A. None
- B. Minimal edema
- C. Non-pitting edema within 4 cm of wound
- D. Non-pitting edema extends beyond 4 cm of wound
- E. Pitting edema within 4 cm of wound
- F. Pitting edema extends beyond 4 cm of wound

Drainage/Exudate:

- A. None
- B. Serosanguinous
- C. Serous
- D. Seropurulent
- E. Purulent

Amount of Drainage/Exudate:

- A. None
- B. Scant (less than 1 ml)
- C. Mild (Less than 25% of dressing saturation)
- D. Moderate (50% to less than 75% of dressing saturation)
- E. Copious (75% or more of dressings saturated)

Tenderness/Pain at Wound Site (pain scale 0-10):

- A. None
- B. 1 to 2
- C. Greater than 3 to 4
- D. Greater than 4 to 7
- E. 8 to 10

Statistical Analysis Plan

Analyses: The primary outcome is wound closure by Week 12, which will be analyzed using Chi-square test to compare the percentages of subjects with complete closure in each group. We will also perform exploratory analysis with logistic regression, using the complete closure at 12 weeks as the dependent variable and the independent variables would include, treatment, size of ulcer, location on foot, how long ulcer has been present, previous revascularization (will analyze as subset group), offloading compliance, concomitant medications, foot deformity, history of amputation, diabetes complications index, CRP level, and glucose control (HbA1c). Selection of covariates will be performed by stepwise modeling procedures, and overseen by biostatistician [name].

Cost effectiveness analysis: We will perform a cost-effectiveness analysis comparing the treatment groups Dermagraft®, Apligraf®, Oasis® and the standard care group at the NCHCS using ANOVA or Kruskal-Wallis test depending if data is normally distributed for comparison of the three treatment arms. If significant, we will further analyze with pair-wise comparisons by using t-test or Wilcoxon rank-sum test with the Bonferroni correction to control for type I experiment-wise error rate of 0.05. A p-value less than $0.05/3 = 0.0167$ will be considered statistically significant.

We will evaluate the cost-effectiveness of the Oasis® compared to Dermagraft® or Apligraf® and the standard of care by measuring QALYs as the measure of effectiveness, based on results obtained from SF-36v2™ questionnaire. Multiple regression will be used to allow to evaluate continuous dependent variable outcomes, including change scores between baseline and end of study physical (PCS) and mental (MCS) component summaries from the SF36v2™ questionnaire.

Rates of healing among the four groups will be analyzed using log-rank test to compare time of healing within 20 weeks.

Secondary outcomes such as complete healing at 20 weeks, recurrence ulceration rate at 20 weeks will be analyzed using Chi-square tests. In addition, demographics, smoking history, and characteristics of the wound will also be summarized in table. For comparison nominal categorical secondary outcome variables, we will use Chi-square test. For comparison of ordinal categorical variables, we will use the Wilcoxon rank-sum test (for two independent group comparison) and Kruskal-Wallis test (for three independent group comparison).
